11.3 STATISTICAL ANALYSIS PLAN

11.3.1 Estimate the PFS for subjects treated on Stratum 1.

Sample size: The primary measure of efficacy will be PFS at 6-months for Stratum 1 patients. In specific, the 6-month PFS for this treatment will be compared to a reference of 15.8% (hazard rate = 0.308/person-month i.e. median of 2.25 months). In patients with metastatic osteosarcoma a 6-month PFS of 35% would be considered promising, and is the benchmark for this study. Assuming exponential survival, 4 patients per year will be accrued for 5 years (20 total), one year of additional follow-up, and a one-sided 0.05 alpha level test, the sample size of 20 will have 82% power to detect a hazard ratio of 1.76.

Early stopping guideline for safety: The study will be monitored after every patient for non-hematologic grade 4 toxicities following initiation of external beam radiation therapy. This stopping rule for toxicity will hold enrollment if the posterior probability of risk being larger than 0.2 is 75% or higher. The prior for this toxicity monitoring rule is beta (1, 5). This distribution means that our prior guess at this type of grade 4 toxicity is 16.7%, and there is 95% probability that it is between 0.51% and 52.2%. The operating characteristics of the stopping rule are shown below and are based on 5000 simulations:

Toxicity stopping rule:

Study termination if:	2 AEs	3 AEs	4 AEs	5 AEs	6 AEs
And number of patients between:	2 - 3	4 - 7	8 - 12	13 - 16	17 - 20

Operating characteristics of stopping rule based on 5000 simulations:

True Toxicity Risk	Prob. Declare Treatment Too Toxic	Avg. Sample Size
0.05	1.0%	19.8
0.10	6.4%	19.2
0.15	17.1%	17.9
0.20	33.7%	16.2
0.25	54.0%	13.8
0.30	69.1%	12.0
0.35	82.9%	9.7
0.40	92.6%	7.9

Early stopping guideline for futility and simulations: Simulation is used to demonstrate the operating characteristics of the study for a sample size of 20. The study will be monitored for futility with a primary endpoint of 6-month PFS. The non-parametric Kaplan-Meier estimate will be used to estimate the PFS function at 6-months. After 8 patients have been enrolled, the design will include an interim analysis for futility that could halt the trial if it seems likely that the treatment does not have sufficient clinical activity.

The sample size of 20 and the study design operating characteristics assume a 5 year accrual period with an additional follow-up of one year. The null 6-month PFS is 15.8%. We have designed the study to stop early only if the posterior probability of 6-month PFS being less than 0.15 is 80% or higher. Simulations were carried out with exponential survival and staggered patient entry. We assume on average 1 patient will enter the study every three months. Interim analyses begin once 8 patients have been entered on the study and occur after groups of 4 patients thereafter up to a maximum of 20 patients. The interim analysis estimates of 6-month PFS are based on analyses with an underlying Dirichlet process prior. We approximate the posterior distribution, which is actually a mixture of Beta distributions, the mixture depending on the amount of censoring, with a single Beta distribution. The parameters of this posterior Beta distribution are based on the number of failures and the effective sample size at 6-months, combined with the parameters of the prior.

The following table summarizes the operating characteristics of the futility stopping rule under various scenarios for the underlying exponential PFS, based on 5000 simulations. For futility monitoring we characterize the uncertainty of the 6-month PFS estimate with the prior: beta (1, 4). This implies that our prior guess at the 6-month PFS in this study is 20% and there is 90% certainty that the 6-month PFS is between 1.3% and 52.7%.

Table 2. Interim monitoring rule operating characteristics

6-month PFS	Prob Stop for Futility	Avg N	Estimated 6-mo PFS	lo 90% Post Int'l	hi 90% Post Int'l
0.10	0.60	14.2	0.07	0.0	0.20
0.15	0.39	16.2	0.12	0.0	0.30

0.20	0.23	17.7	0.18	0.0	0.35
0.25	0.12	18.7	0.23	0.0	0.40
0.30	0.07	19.2	0.29	0.0	0.45
0.35	0.04	19.6	0.34	0.15	0.50
0.40	0.02	19.8	0.40	0.20	0.60

Analysis for primary objective: Overall hazard rate estimates and 95% confidence intervals as well as Kaplan-Meier (KM) estimates will be used to summarize PFS over time. The 6-month PFS with 95% confidence interval will be reported.

11.3.2 Describe the toxicity profile of this regimen in the short and long-term.

Toxicities will be graded according to CTCAE v4.0 and the RTOG Cooperative Group Common Toxicity Criteria, and attributable toxicities grade 3 or higher will be recorded. For purposes of evaluation, we will consider toxicities resulting from the administration of ¹⁵³Sm-EDTMP separately from toxicities resulting after initiation of external beam radiation therapy. [However, we will hold accrual after enrollment of five patients to evaluate cumulative toxicity from the combined regimen.] Adjustments to external beam therapy in response to toxicity would be made in accordance with standard Radiation Oncology treatment protocols and clinical judgment.

11.3.3 Describe the distribution of absorbed doses delivered to each targeted lesion and the distribution of equivalent uniform doses delivered to each patient.

The total absorbed dose delivered to each targeted lesion will be limited by the tolerance of surrounding normal tissue. We will produce histograms showing the distribution of radiation absorbed doses by lesion, and summarize the results by patient for the lesion receiving the lowest absorbed dose in each patient. With a sample size of 20 patients, we will be able to estimate the proportion of patients whose lesions are all treated to an absorbed dose of ≥ 80 Gy with a precision of $\pm 23\%$.

11.3.4 Model the relationship between absorbed dose and time to progression for patients enrolled in Stratum 1.

We expect a total dose of 80 to 100 Gy to produce a local control rate of 80%, while a total absorbed dose of 60 to 70 Gy may produce a local control rate of 50 – 70%, and the local control rate would decline steeply at lower absorbed doses. We will use a generalized mixed effects model treating dose and time as fixed effects and the random effect of individual patients for the outcome of progression of each targeted lesion. If at least 10 patients have at least one lesion that receives a radiation dose with similar effectiveness to our historical control experience, and at least one lesion receiving the targeted dose, this analysis would have 80% power to demonstrate a significant dose-response with alpha 0.05.

11.3.5 Determine overall and progression-free survival for patients enrolled in Stratum 1.

Survival curves will be estimated by using the Kaplan-Meier method. Progression-free survival is defined as time from registration to the first observation (documentation) of disease progression or death. Patients who are lost to follow-up will be censored for determination of PFS on the date of their last evaluations. Overall survival is defined as time from registration to death due to any cause.

11.3.6 Determine correlation of hypoxic volume and maximum tumor/blood ratio obtained by [¹⁸F]-MISO PET scanning with patient outcomes.

Cox regression analysis will be performed to measure association between hypoxia based on HV and max T/B ratio with Kaplan-Meier survival and time-to-progression curves. Additional regression analysis will be performed to evaluate the link between hypoxic indices and uptake of ¹⁵³Sm-EDTMP and clinical response based on radiologic response and presence of necrosis on histology.

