12.0 DATA RECORDING, MANAGEMENT, AND MONITORING

12.01 To register eligible patients on study, the investigator will fax the completed registration form to the Johns Hopkins Oncology center Clinical Research Office at [contact].

12.02 Informed consent must be signed by the patient or in the case of a minor, the parent or legal guardian.

12.03 If a patient does not receive protocol therapy, the patient is removed from protocol. Reasons for cancellation must be submitted in writing to the Principal Investigator. Once a patient has been given protocol treatment, all forms must be submitted.

12.04 Case report forms, including dosimetry, toxicity and response evaluation will be completed in a timely manner.

12.05 This is a DSMP Level I study under the SKCCC Data Safety Monitoring Plan (12/6/2012). The Clinical Research Office QA Group will perform an audit after the first subject has been treated and then periodically depending on the rate of accrual and prior audit results. All trial monitoring and reporting will be reviewed annually by the SKCCC Safety Monitoring Committee.

The PI is responsible for monitoring the study. Data must be reviewed to assure the validity of data, as well as, the safety of the subjects. The PI will also monitor the progress of the trial, review safety reports, and clinical trial efficacy endpoints and to confirm that the safety outcomes favor continuation of the study.

The PI will be responsible for maintaining the clinical protocol, reporting adverse events, assuring that consent is obtained and documented, reporting of unexpected outcomes, and reporting the status of the trial in the continuing renewal report

submitted to the IRB and to the trial monitoring review group. Content of the continuing renewal report at a minimum should include year-to-date and full trial data on: accrual and eligibility, protocol compliance, treatment administration, toxicity and ADR reports, response, survival, regulatory compliance, compliance with prearranged statistical goals. The report should be submitted in a timely manner according to the schedule defined by Johns Hopkins Medicine Institutional Review Board.

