12.1.2 Investigator's Reporting Obligations

12.1.2.1 Grade 4 (life-threatening) or grade 5 (fatal) adverse events that are unexpected (no listed on the package label) with an attribution of possible, probable, or definite must be reported to the FDA within 10 business days.

12.1.2.2 Reports to the FDA should be submitted in writing (FDA Form 3500 MEDWATCH) to:

[name]
[name] 20993
Ph. [name]
[contact]
www.fda.gov/medwatch

with a copy simultaneously submitted to the Johns Hopkins Institutional Review Board.

12.1.2.3 Johns Hopkins Institutional Review Board reporting requirements: The Organization has the responsibility to report unanticipated problems involving

risk to subjects or others under [Policy 103.6\(b\)](#), serious or continuing non-compliance under [Policy 103.7](#), and suspension or termination of approved research under [Policy 113.1](#), to the appropriate agencies. The Institutional Official (IO) is authorized as the individual who will submit reports when an IRB has made a determination under the three cited policies. In cases where the IRB and IO determine that additional information is required before submitting a final report, a preliminary report may be made to the appropriate officials, supporting federal agency (as applicable), OHRP, and FDA (as applicable), within one month of the IRB's determination.

12.1.2.4 A draft preliminary or final report will be prepared for review by the IO and General Counsels (GCs). The draft report will contain the following information:

- The nature of the event
- The findings of the organization
- The actions taken by the organization and IRB, including plans to protect the rights and welfare of the participants
- The reasons for the organization's and IRB's actions
- The plans for continued oversight or investigation or action.

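### The only numeric toxicity boundary is defined on grade 4 events, so read literally it leaves out a non-hematologic toxicity graded 5 directly

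*Combined protocol and SAP*

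**What the plan says.** Section 11.3.1, under the early stopping guideline for safety, sets the monitored event: "The study will be monitored after every patient for non-hematologic grade 4 toxicities following initiation of external beam radiation therapy". The action and threshold follow: "This stopping rule for toxicity will hold enrollment if the posterior probability of risk being larger than 0.2 is 75% or higher". The prior is Beta(1,5), glossed as "our prior guess at this type of grade 4 toxicity is 16.7"%, so the grade 4 definition appears twice. The boundary table below it counts AEs without naming a grade, and its first row is labelled "Study termination if".

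Elsewhere the protocol uses inclusive wording when it means a range. Section 11.3.2 says that "attributable toxicities grade 3 or higher will be recorded". Section 12.1.2.1 names the two top grades separately: "Grade 4 (life-threatening) or grade 5 (fatal) adverse events that are unexpected". Section 12.2 refers back to 11.3.1 for the safety rule and adds only a provision on hospitalization; it does not widen the event to grade 5.

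Other provisions also touch fatal toxicity. Section 11.3.2 states that "we will hold accrual after enrollment of five patients to evaluate cumulative toxicity from the combined regimen". Section 12.05 has the principal investigator (PI) review safety reports and efficacy endpoints to "confirm that the safety outcomes favor continuation of the study", with annual review by the Safety Monitoring Committee. Section 12.1.2 requires expedited reporting and immediate notice of a fatal toxicity to the PI. Section 12.2 adds ongoing data review and committee monitoring. Section 11.2 makes death from any cause a progression-free survival (PFS) event in Stratum 1, so deaths there feed the futility rule.

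**The concern.** The rule is applied by count after every patient. If the count covers grade 4 only, the most severe outcome adds nothing to it unless the same event was first recorded as grade 4. A team following the text could read off continue after deaths that would have crossed the boundary had they been counted. The decision would then rest on review without a stated limit. Whether a directly fatal event counts should be settled in advance, not argued once one has happened.

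**Working it through.** **Inputs (Section 11.3.1).** Prior Beta(1,5); boundary crossed if P(risk > 0.2 | data) ≥ 0.75; checked after each patient up to 20. The documents give neither a fatal toxicity rate nor the share of fatal events first recorded as grade 4, so both are assumed below.

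**1. Reproduce the plan's rule.** With x events in n patients the posterior is Beta(1+x, 5+n−x), and

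P(risk > 0.2) = P(Bin(n+5, 0.2) ≤ x).

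The smallest x reaching 0.75 is 2 for n = 2–3, 3 for n = 4–7, 4 for n = 8–12, 5 for n = 13–16 and 6 for n = 17–20. This matches the plan's table in every row. Exact recursion over n = 1 to 20 gives:

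| True risk | P(stop), exact | P(stop), plan | Average N, exact | Average N, plan |
|---|---|---|---|---|
| 0.10 | 6.2% | 6.4% | 19.2 | 19.2 |
| 0.15 | 17.4% | 17.1% | 17.9 | 17.9 |
| 0.20 | 34.1% | 33.7% | 16.1 | 16.2 |

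The differences are consistent with 5000 simulations. The arithmetic of the rule is sound; the question is only which events enter x.

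**2. Two directly fatal toxicities in the first 3 patients** (n + 5 = 8).

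- Neither counted, x = 0: 0.8^8 = 0.168. Continue.
- One first graded 4, x = 1: 0.168 + 8(0.2)(0.8^7) = 0.168 + 0.336 = 0.503 after rounding. Continue.
- Both counted, x = 2: 0.503 + 28(0.2²)(0.8^6) = 0.503 + 0.294 = 0.797. Boundary crossed.

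The middle line shows the scope of the gap: it concerns events graded 5 directly. A fatal toxicity first recorded as grade 4 counts under the present wording.

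**3. Effect on the chance of stopping.** Let g be the grade 4 risk, f the additional risk of a fatal toxicity, and h the share of fatal events first graded 4. The risk the rule sees is g + h·f. With assumed g = 0.10 and f = 0.025:

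| Counting | Risk seen by the rule | P(stop) | Average N |
|---|---|---|---|
| h = 0, as written, lower limit | 0.10 | 6.2% | 19.2 |
| h = 0.5, as written | 0.10 + 0.5 × 0.025 = 0.1125 | 8.4% | 18.9 |
| All fatal events counted | 0.10 + 0.025 = 0.125 | 11.0% | 18.6 |

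For larger assumed fatal risks of 5% and 10%, still with g = 0.10, counting all gives 17.4% and 34.1%, against 6.2% at h = 0 and 11.0% and 17.4% at h = 0.5.

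**4. Does the futility rule fill the gap?** It stops if the posterior probability of 6-month PFS below 0.15 is at least 80%, with prior Beta(1,4). With complete follow-up, 0 of 8 patients progression-free gives 1 − 0.85^12 = 0.858, which stops. So a numeric threshold that includes deaths does exist. But it is an efficacy boundary that pools deaths with progression, covers Stratum 1 only, and is first applied at 8 patients. It cannot act in the 3-patient case of step 2.

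**The case against.** The strongest reply is that nobody would count a life-threatening toxicity and ignore a fatal one. The boundary table says only AEs, its columns speak of toxicity risk in general, and the text calls itself a guideline. As to intent, this probably stands, and it is why the point is minor. It does not settle the text: the table takes its event from the sentence above it, and the protocol writes the wider range elsewhere when it wants it.

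A second reply is that the size is assumed. That also stands. The protocol's background reports toxicity limited to hematologic suppression in its own 11 patients and myelosuppression as the sole toxicity in 30 others. Neither experience is with this combined regimen, so neither bounds its fatal risk, but nothing in the documents supports a high rate of direct non-hematologic deaths. Two in three patients is an illustration, not a forecast.

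A reader might infer that toxic deaths would go unchecked. The documents do not support that: the five-patient hold, PI and committee review, expedited reporting and immediate notice to the PI all apply, and in Stratum 1 deaths enter a numeric futility rule. Accrual of about one patient every three months also leaves time to act.

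A reader might also take the five-week hospitalization wording in Section 12.2 as contradicting 11.3.1 on when counting starts. It does not; it concerns when a hospitalization makes an event serious, while 11.3.1 counts by grade from the start of external beam treatment.

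**Conclusion.** The event definition is wrong as written, with minor severity. Section 11.3.1 sets the trial's only numeric toxicity boundary on grade 4 events, and no section brings a directly graded 5 event into the count. The other safeguards remain, but none is a numeric toxicity limit.

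The posterior figures (0.168 against 0.797) follow from the plan's own prior and threshold and need no outside input. The change in stopping probability, from between 6.2% and 8.4% to 11.0%, rests on an assumed 10% grade 4 risk and 2.5% fatal risk, and on how many fatal events were first graded 4.

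Separately, 11.3.1 says in its text that crossing the boundary holds enrollment, and in its table that the study terminates. One might infer from the published average sample sizes that termination is meant, since they match enrollment ending at the boundary. They do not show this: a hold that is never lifted gives the same averages. The mismatch stands on the wording alone.

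**What to change.** In 11.3.1, write *non-hematologic grade 4 or higher (grade 4 or 5) toxicities* in the rule, and use the same event in the sentence describing the prior. Have the team confirm that Beta(1,5) and the 0.2 limit express its view for that wider event. If they are kept, the boundary table and operating characteristics stay as they are, because they depend only on the probability of the counted event. If the team preferred Beta(1,4), with mean 20%, the boundary ranges would shift by only one patient: 2 events at n = 2–4, 3 at 5–8, 4 at 9–13, 5 at 14–17 and 6 at 18–20.

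Separately, reconcile the text and the table of 11.3.1 on the action taken when the boundary is crossed.

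The cost is a short amendment; attributable events of grade 3 or higher are already recorded. The downside is a somewhat higher chance of crossing the boundary: under the assumed rates, 11.0% instead of 6.2% to 8.4%, with average sample size 18.6 instead of 19.2 to 18.9.

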6.2 OVERALL TREATMENT PLAN

This is a treatment protocol to establish the safety and efficacy of radiation therapy consisting of high-dose ^{153}Sm -EDTMP and external beam radiotherapy for the treatment of high-risk osteogenic sarcoma and solid tumors with bony metastases. The primary endpoint will be clinical response of tumor lesions, defined as either stable disease or decrease in the size of the tumor by radiographic imaging (which may include CT or MRI) using RECIST 1.1 criteria. Progression will be defined as appearance of new lesions or expansion of current lesions by 20% as per RECIST 1.1 criteria. In some patients, additional information on clinical response may be obtained from histology (percent tumor necrosis) in cases where patients proceed to resection or biopsy following radiation therapy. Other treatment endpoints include progression-free and overall survival. We will obtain post-treatment [^{18}F]-MISO and [^{18}F] FDG PET scans to be analyzed but these images will not be used to define clinical response.

The first administered activity of ^{153}Sm -EDTMP will be a low “tracer” infusion administered at 1 mCi/kg on Day 1. Using the 3-dimensional dosimetry package 3D-RD, we will perform three-dimensional dosimetry using SPECT images after administration of the “tracer” activity to determine the distribution of dose delivered to the tumor and the surrounding normal tissues. As quickly as feasible (goal is within seven days), using the dosimetric results from the tracer administration, a combined treatment plan will be designed aimed at delivering the target dose to the entire tumor. This plan will be designed using methodology uniquely available at Hopkins (3D-RD software); we will import the 3-dimensional absorbed dose map resulting from ^{153}Sm -EDTMP therapy, adjusted to correspond to the fractionation schedule used in external beam radiotherapy, into the external beam planning system (Pinnacle), by fusing (registering) the SPECT/CT and absorbed dose map with the external beam planning CT, allowing a treatment plan to be generated from the combination of (1) scaling of the tracer absorbed dose map to the requisite ^{153}Sm therapeutic activity and (2) external beam fields designed to optimally complement the radiopharmaceutical absorbed dose map to deliver a target of 75 Gy to each and every tumor voxel while respecting normal organ constraints (25).

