The first portion of the combined plan, that is, the second, “treatment” ^{153}Sm -EDTMP infusion, will then be implemented on Day 8. Maximum activity administered will be 30 mCi/kg, which is the maximally tolerated dose permitting recovery of myelosuppression with auto-stem cell infusion (14). After the “treatment” infusion, SPECT scans will again be performed to confirm total dose delivered and subsequently adjust the external beam portion of the treatment plan, as necessary. External beam radiotherapy will begin as early as possible between Days 15 and 22. The total dose to be used will be modified based on surrounding tissue tolerances. On Day 24, previously harvested autologous peripheral blood or bone marrow stem cells will be infused in order to ameliorate the expected myelosuppression. External beam radiation therapy will not be administered on Day 24 (anticipated to be a Friday), nor on Days 25 or 26, in order to provide time for infused hematopoietic stem cells to home to the bone marrow and leave the circulation.

Patients will be reimaged one month following completion of external beam radiation by CT/MRI for evidence of clinical response (defined as stable disease or better by RECIST 1.1 criteria) or disease progression. In the event of progression of a single lesion, local therapy such as radiofrequency ablation or cryoablation may be provided so that the response of stabilized lesions can continue to be monitored. If suspicious lesions remain on

thoracic CT scan or on MRI of the primary site after the completion of therapy, further evaluation by biopsy may be clinically indicated, and potentially surgical intervention pursued if persistent disease is found. Percent necrosis of any resected tumor will be evaluated pathologically.

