11.0 STATISTICAL CONSIDERATIONS

11.1 OVERVIEW

This protocol will assess the proportion of clinical tumor responses, defined as progression-free survival at 6 months, and the toxicities associated with high-dose ^{153}Sm -EDTMP (MTD at 30 mCi/kg) after an initial lower dose of the agent along with external beam radiation therapy in patients with high-risk osteogenic sarcoma.

Primary objective: The primary objective of this study is to determine if the addition of external beam radiation therapy to infusional ^{153}Sm -EDTMP can delay the progression of target lesions. The primary endpoint is 6-month progression free survival (PFS). It is a combined effect of the entire treatment. To be evaluable, patients must meet all eligibility criteria, including signing a consent form, and have completed treatment according to protocol without major deviations. Patients who are enrolled but unevaluable will be replaced on the study. Only patients enrolled on Stratum 1 (i.e., with a diagnosis of osteosarcoma) will be evaluated for the Primary Objective.

Secondary objectives:

1. Describe the short and long-term toxicity profile of combined treatment with ^{153}Sm -EDTMP and external beam radiation therapy.
2. Estimate the local control rate. (Stratum 1 only)
3. Determine the overall survival (OS). (Stratum 1 only)
4. Describe the distribution of absorbed doses delivered to each targeted lesion and the distribution of equivalent uniform doses delivered to each patient.
5. Model the relationship between absorbed doses and time to progression.
6. Determine the correlation of hypoxic volume and maximum tumor/blood ratio obtained by [^{18}F]-MISO PET scanning with patient outcomes.

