12.2 EARLY STOPPING RULE

Data will be reviewed on an ongoing basis. An early stopping rule for safety is described above (Section 11.3.1). For the stopping rule, the requirement for hospitalization in the first five weeks after samarium for temporary hematopoietic, infectious, or GI toxicities will not *per se* be considered a defining criterion of seriousness of an adverse event.

This is a Level 1 study under the SKCCC CRO Data and Safety Monitoring Plan. Data monitoring of this protocol will occur on a regular basis with the frequency dependent on

the rate of subject accrual and the progress of the study. Trial monitoring and reporting will be done through the Clinical Research Review and Monitoring Committee (CRC).

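### The only numeric toxicity boundary starts counting at external beam radiotherapy, so non-hematologic grade 4 events with onset between the first samarium infusion and that point are not counted

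*Combined protocol and SAP*

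**What the plan says.** Section 6.2 describes the aim as a whole-regimen one: "This is a treatment protocol to establish the safety and efficacy of radiation therapy consisting of high-dose" samarium together with external beam radiotherapy. The tracer infusion (1 mCi/kg) is on Day 1 and the treatment infusion (at most 30 mCi/kg) on Day 8. Then: "External beam radiotherapy will begin as early as possible between Days 15 and 22".

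Section 11.3.1 gives the safety guideline. Its window is: "The study will be monitored after every patient for non-hematologic grade 4 toxicities following initiation of external beam radiation therapy". Its criterion is: "This stopping rule for toxicity will hold enrollment if the posterior probability of risk being larger than 0.2 is 75% or higher". The prior is Beta(1,5). A table gives the number of events that triggers the rule for 2 to 20 patients, and a second table gives operating characteristics by true risk.

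Section 11.3.2 evaluates samarium toxicity "separately from toxicities resulting after initiation of external beam radiation therapy" and adds an accrual hold after five patients to look at cumulative toxicity. It gives no numeric limit for either. Section 12.2 points back to 11.3.1. It adds that, for the stopping rule, "the requirement for hospitalization in the first five weeks after samarium for temporary hematopoietic, infectious, or GI toxicities" does not in itself make an event serious. Section 6.3.3 names renal and bladder toxicity as a risk of samarium excretion.

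**The concern.** The boundary is restricted by when an event begins. Two infusions of the investigational agent, one of them at up to 30 mCi/kg, come before the window opens. A renal or bladder event of grade 4 in that interval, which is non-hematologic and of the kind 6.3.3 tells sites to watch for, adds nothing to the count.

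The patients most affected by samarium are also those least likely to reach external beam. If such a patient stays in the boundary's denominator, a severe early event is scored as a non-event and makes stopping slightly less likely. If the patient is left out, the event disappears from the calculation. The plan does not say which applies.

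At stake is the meaning of the operating-characteristics table. As written, its true risk refers only to the part of treatment after external beam starts. The trial could pass its safety rule while the risk from first infusion exceeds the plan's own 0.2 limit.

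**Working it through.** **Uncounted time.** External beam starts on Days 15 to 22 (6.2). From the tracer on Day 1 this is 15 − 1 = 14 to 22 − 1 = 21 days. From the treatment infusion on Day 8 it is 15 − 8 = 7 to 22 − 8 = 14 days.

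**Reproducing the plan's boundary.** Inputs from 11.3.1: prior Beta(1,5), limit 0.2, criterion 75%. After x events in n patients the posterior is Beta(1 + x, 5 + n − x). The boundary is the smallest x with Pr(risk > 0.2) ≥ 0.75. For example, 3 events in 7 patients give 0.795 (trigger), 3 in 8 give 0.747 (no trigger) and 4 in 8 give 0.901 (trigger). The result for every n is 2 events at 2–3 patients, 3 at 4–7, 4 at 8–12, 5 at 13–16 and 6 at 17–20, as printed.

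**Reproducing the operating characteristics.** An exact recursion over patients 1 to 20 gives stopping probabilities of 1.1%, 6.2%, 17.4% and 34.1% at true risks 0.05, 0.10, 0.15 and 0.20. The plan prints 1.0%, 6.4%, 17.1% and 33.7%. All eight printed values agree within 1.2 points. The arithmetic is sound; the gap is in which events enter it.

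**Effect of the window.** Let s be the per-patient risk of a non-hematologic grade 4 event before external beam and e the risk after it starts, taken as independent. The whole-regimen risk is t = 1 − (1 − s)(1 − e). Neither s nor e is in the documents. I take e = 0.15 and let s run from 0 to 0.10.

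| Early risk s | Regimen risk t | Stop, as written | Stop, all events counted |
|---|---|---|---|
| 0 | 0.150 | 17% | 17% |
| 0.02 | 1 − 0.98 × 0.85 = 0.167 | 17% | 23% |
| 0.05 | 1 − 0.95 × 0.85 = 0.1925 | 17% | 31% |
| 0.10 | 1 − 0.90 × 0.85 = 0.235 | 17% | 47% |

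With e = 0.20, the rule as written stops with 34%. Counting all events gives 40% at s = 0.02 (t = 0.216) and 64% at s = 0.10 (t = 0.28).

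**Effect of the undefined denominator.** The as-written column assumes that patients with an early event still start external beam. If instead they never start but stay in the denominator, the counted risk is e(1 − s). At e = 0.15 and s = 0.10 this is 0.135, and the chance of stopping falls from 17% to 13%.

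**Extension beyond 20 patients.** The same formula gives 7 events at 21–25 patients: 6 in 21 gives 0.747, 7 in 21 gives 0.869, 7 in 25 gives 0.761 and 7 in 26 gives 0.730.

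**The case against.** The strongest reply is that the window is deliberate. The new element is external beam; high-dose samarium had already been studied. Section 4.3 cites a 30-patient trial with a maximum tolerated dose of 30 mCi/kg in which myelosuppression was the only toxicity reported, and the group's own 11-patient tandem-dosing study with toxicity limited to hematologic suppression. Read as 0 of 41, this gives a one-sided 95% upper bound of 1 − 0.05^(1/41) = 7.0%, or 9.5% for the 30 alone, with the caveat that not all received 30 mCi/kg. This stands as a reason to expect a low early risk, and the 10% row lies above both bounds. It does not justify leaving the interval without a limit: if the risk is low, counting those days costs almost nothing.

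It also stands that the period is not unmonitored. There is weekly evaluation (6.3.2), discretionary removal (9.2), the five-patient hold (11.3.2), annual committee review (12.05), expedited reporting of unexpected attributable grade 4–5 events (12.1.2.1) and ongoing review (12.2). None has a threshold for the trial as a whole.

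Three stronger readings are tempting but not supported.

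- A reader might infer that severe samarium toxicity can never trigger the rule. The rule restricts by timing and not by attribution, so samarium-related events with onset after external beam starts do count. Hematologic toxicity is excluded throughout.
- A reader might infer that Section 11.1 drops the early patients from safety assessment, because "Patients who are enrolled but unevaluable will be replaced on the study". That sentence sits in the paragraph on the primary endpoint, and no section removes them from toxicity evaluation.
- A reader might infer that 12.2 contradicts 11.3.1. Five weeks from Day 8 runs to Day 43 (8 + 35), which overlaps the counted window by 21 to 28 days. The clause has meaning under 11.3.1 as written; it is ambiguous about the period covered.

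**Conclusion.** The gap is real on the plain text. Non-hematologic grade 4 events with onset in the 14–21 days after the tracer, including the 7–14 days after the treatment infusion, fall outside the only numeric boundary, and the handling of patients who never start external beam is undefined. With an after-start risk of 0.15, the loss in the chance of stopping runs from nothing at zero early risk, through about 5 points at 2% and 14 at 5%, to 30 at 10%. Those figures rest on assumed risks, on independence of the two phases and on a maximum of 20 patients. The lower rows are the more plausible given the cited experience.

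This should be fixed. A reader might rate it as a defect that must be corrected before the trial can proceed. The deliberate split by phase, the unquantified safeguards and the likely low early risk do not support that.

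**What to change.** In 11.3.1, count qualifying non-hematologic grade 4 events from the first samarium infusion, and state that every patient who received any samarium is in the denominator whether or not external beam is started. Keep the 0.2 limit and the 75% criterion. Keep the Beta(1,5) prior, or confirm that it also suits the wider event, since it was stated for events after external beam starts. If more than 20 patients are infused, extend the boundary by the same formula (7 events at 21–25). Reconcile the period named in 12.2 with this window. The descriptive split by phase in 11.3.2 can stay.

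The cost is about one sentence in each of 11.3.1 and 12.2. No new data are needed, because Table 1 and 6.3.2 already provide evaluations through this period. The operating-characteristics table is indexed by true risk and stays valid. The downside is a higher chance of holding enrollment when the total risk is just below 0.2: 31% instead of 17% at a total risk of 0.1925 (0.15 after the start and 0.05 before it).
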